7.4. Safety Endpoint

Safety endpoints will include incidence of treatment-emergent and treatment-related AEs and changes from Baseline in ECG parameters, safety laboratory parameters, physical exams, and vital signs. The SAFT Population will be used for descriptive summaries of the safety endpoints.

7.4.1. Adverse Events (AEs)

AEs will be coded to system organ class (SOC) and preferred term (PT) using the Medical Dictionary for Regulatory Activities (MedDRA). The number and percentage (incidence) of subjects reporting an AE and the number of AEs will be summarized. A treatment-emergent AE will be defined as AEs that started at or after the first injection.

The following AE incidence tables will be provided for treatment-emergent AEs:

- AE Profile Overview
- Treatment-Emergent AEs by SOC and PT
- Treatment-Related AEs by SOC and PT
- Treatment-Emergent SAEs by SOC and PT
- Treatment-Related SAEs by SOC and PT
- Unexpected Adverse Drug Reactions by SOC and PT
- Adverse Events of Special Interest by SOC and PT

Treatment-related AEs will be defined as possibly, probably, or definitely related. Two-sided Wilson 95% confidence intervals will be calculated for the overall incidence of AEs and SAEs.

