### 10.2.5 Visits 5 to 15 (Visits each 30 Days; V5 $\pm$ 3 days, V6 to V15 $\pm$ 7 days)

Subjects will continue to be monitored for safety and effectiveness at one-month intervals. On and after **Day 90**, subjects are eligible to exit the study once their GLS score at maximum frown has returned to Baseline (Investigator assessment). Subjects will return for monthly assessments until they reach their Baseline GLS score (Investigator assessment). Assessment procedures include:

- Brow Area Photography
- Effectiveness Evaluations Investigator (Blinded Evaluator)
  - GLS (max frown)
  - GAIS
- Effectiveness Evaluations Subject
  - GLS (max frown)
  - GAIS
  - Subject Satisfaction
  - Clinical Interview (Visit 5; Day 30 only) (Section 10.3.4)
- Safety Assessments Investigator (Blinded Evaluator)
  - Directed Questionnaire
  - Directed Review of Systems
  - Vital Signs
  - Physical Exam
  - Concomitant Medications
  - Adverse Events

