#### 12.5.1 Adverse Events (AEs)

AEs will be coded to system organ class (SOC) and preferred term (PT) using the Medical Dictionary for Regulatory Activities (MedDRA). The number and percentage (incidence) of subjects reporting an AE and the number of AEs will be summarized.

A treatment-emergent AE will be defined as AEs that started at or after the first injection.

The following AE incidence tables will be provided for treatment-emergent AEs:

- All AEs by SOC and PT
- Related AEs by SOC and PT
- All AEs by PT sorted by decreasing frequency among all subjects
- Related AEs by PT sorted by decreasing frequency among all subjects
- All SAEs by seriousness criterion
- Related SAEs by seriousness criterion

- All SAEs by SOC and PT
- Related SAEs by SOC and PT

Treatment-related AEs will be defined as possibly, probably, or definitely related. Two-sided Wilson 95% confidence intervals will be calculated for the overall incidence of AEs and SAEs.

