1.4. Study Objectives

The primary objectives of this study are to demonstrate the safety and duration of effect of 40U of prabotulinumtoxinA-xvfs in providing temporary improvement in the appearance of moderate to severe glabellar lines associated with corrugators and/or procerus muscle activity in adult subjects.

Confidential Page 8/58

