2. OVERVIEW OF STUDY DESIGN

2.1. Study Design

This is a multicenter, prospective, randomized, double-blind, active-controlled, single-treatment, increasing dose design.

Approximately 150 subjects will be randomized 1:1:1, to either 20U onabotulinumtoxinA, 20U prabotulinumtoxinA-xvfs, or 40U prabotulinumtoxinA-xvfs. Subjects with moderate or severe glabellar lines at maximum frown on the 4-point validated Glabellar Line Scale (*GLS*, 0=none, 1= mild, 2=moderate, 3=severe), as judged by the investigator and the subject, will be eligible.

Safety and effectiveness will be assessed on days 3, 7, and 30, then every 30 days up to 365 days or until the subject has returned to Baseline as assessed by the Investigator, at which point the subject will exit the study. Please refer to Table 1 below for visit specifics.

Duration of effect will be estimated by Kaplan-Meier analysis and will be based on the number of days from Treatment Day (Baseline) to the day that GLS severity (Investigator assessment) at maximum frown returns to the Baseline value (i.e., the treatment will be considered to remain effective for the amount of time during which GLS severity at maximum frown has not returned to Baseline severity).

The Evaluating Investigator (i.e., Blinded Investigator) will be responsible for managing the subject, monitor for related and unrelated adverse effects, and carrying out the evaluations. Injections of study drug will be performed by an "Unblinded Injector" (i.e., physician or nurse practitioner not responsible for subject follow-up).

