2.3. Primary Endpoint

The primary effectiveness endpoint will be duration of effect, defined as the number of days from Treatment Day (Baseline) to the day that GLS severity (Investigator assessment) at maximum frown returns to the Baseline value. The treatment will be considered to remain effective for the amount of time during which GLS severity at maximum frown has not returned to Baseline severity. Duration of effect will be estimated by Kaplan–Meier analysis.

Although the trial is not powered for inferential analysis, this will be the most influential outcome in the overall assessment of the effectiveness of prabotulinumtoxinA 40 Units, compared to prabotulinumtoxinA 20 Units, in treating moderate to severe glabellar lines.

Confidential Page 9/58

TABLE 1. SCHEDULE OF EVENTS AND PROCEDURES

Visit Number	V1 ¹ Screening	V2 ¹	V3	V4 (phone f/u)	V5 to V15 ²	V16 ³ (or Final Visit, or ET)	Unscheduled Visit 11
Day/Week/Month	≤ 14D	Tx Day	48Hr	D 7	D30 to D330 Monthly Visits	D365	
Visit Windows				±1 Day	D30 ±3D, ≥D60 ±7D	±14D	
Assessment and Procedures							
Informed Consent	X						
Inc/Excl Criteria	X						
Demographics, Med Hx	X						
Randomization to Study Tx 4		X					
Effectiveness - Investigator							
Glabellar Line Scale ⁵	X	X	X		X	X	X
Global Aesthetic Improvement			X		X	X	X
Effectiveness - Subject							
Glabellar Line Scale ⁵	X	X	X		X	X	X
7-Day Subject Diary		Х —		—			
Global Aesthetic Improvement			X		X	X	X
Subject Satisfaction Score			X		X	X	X
Clinical Interview 6					D30 only	X	X
Safety Evaluations							
Directed Questionnaire ⁷	X		X		X	X	X
Directed Review of Systems	X		X		X	X	X
Vital Signs 8	X		X		X	X	X
Physical Exam 9	X		X		X	X	X
UPT (as applicable)	X	X				X	
Clinical Laboratory Tests 10	X					X	X
ECG	X					X	X
Safety Assessment Phone Call				X			
Brow Area Photography	X	X	X		X	X	X
Concomitant Medications	X	X	X	X	X	X	X
AE Assessment		X	X	X	X	X	X

- 1. Screening and treatment visit can take place the same day, at the discretion of the investigator
- 2. Subjects will be followed monthly until their Glabellar Line Scale score is back to Baseline (Investigator assessment)
- 3. Subject exits study once their Glabellar Line Scale Score has returned to Baseline (Investigator assessment)
- 4. IP may be administered same day as Screening
- 5. Glabellar Line Scale at Maximum Frown, 0=none, 1=mild, 2=moderate, 3=severe
- 6. Clinical Interview Questions
 - What did you like about the treatment (clinically or other feedback)?

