14.4 Safety Data

14.4.1 Adverse Events

Table 14.4.1.1 Adverse Event Profile Overview

		PraB 40	PraB 20	OnaB 20
Adverse Events – All Subjects		$(\mathbf{n} = \mathbf{x}\mathbf{x})$	$(\mathbf{n} = \mathbf{x}\mathbf{x})$	$(\mathbf{n} = \mathbf{x}\mathbf{x})$
Participants with any TEAE ^a	Participants	xx (xx.x%) [xx.x, xx.x]	xx (xx.x%) [xx.x, xx.x]	xx (xx.x%) [xx.x, xx.x]
	Events	XXX	XXX	XXX
	Events/Participants	XXX	XXX	XXX
Participants with any TRAE ^b	Participants	xx (xx.x%) [xx.x, xx.x]	xx (xx.x%) [xx.x, xx.x]	xx (xx.x%) [xx.x, xx.x]
	Events	XXX	XXX	XXX
	Events/Participants	XXX	XXX	XXX
Participants with SAE ^c	Participants	xx (xx.x%) [xx.x, xx.x]	xx (xx.x%) [xx.x, xx.x]	xx (xx.x%) [xx.x, xx.x]
	Events	XXX	XXX	XXX
	Events/Participants	XXX	XXX	XXX
Participants with any TRSAE ^d	Participants	x (xx.x%) [xx.x, xx.x]	xx (xx.x%) [xx.x, xx.x]	xx (xx.x%) [xx.x, xx.x]
	Events	XXX	XXX	XXX
	Events/Participants	XXX	XXX	XXX
Participants with UADRe	Participants	xx (xx.x%) [xx.x, xx.x]	xx (xx.x%) [xx.x, xx.x]	xx (xx.x%) [xx.x, xx.x]
	Events	XXX	XXX	XXX
	Events/Participants	XXX	XXX	XXX
Participants with AESIf	Participants	xx (xx.x%) [xx.x, xx.x]	xx (xx.x%) [xx.x, xx.x]	xx (xx.x%) [xx.x, xx.x]
	Events	xxx	XXX	XXX
	Events/Participants	XXX	XXX	XXX

95% CI [xx.x, xx.x]. aTEAE= Treatment-Emergent AE. bTRAE= Treatment-Related AE. cVADR= Unexpected Adverse Drug Reaction. AESI= Adverse Effect of Special Interest. Number of Participants (% in parenthesis).

Confidential Page 51/58

Table 14.4.1.2 Treatment-Emergent Adverse Events Sorted by SOC and PT

		PraB 40 (n = xx)		PraB 20 (n = xx)		OnaB 20 (n = xx)	
SOC	PT	Participants	Events	Participants	Events	Participants	Events
Any TEAE		xx (xx.x%) [xx.x, xx.x]	XX	xx (xx.x%) [xx.x, xx.x]	XX	xx (xx.x%) [xx.x, xx.x]	XX
XXXXXXX		xx (xx.x%) [xx.x, xx.x]	XX	xx (xx.x%) [xx.x, xx.x]	XX	xx (xx.x%) [xx.x, xx.x]	XX
	XXXXXXX	xx (xx.x%) [xx.x, xx.x]	XX	xx (xx.x%) [xx.x, xx.x]	XX	xx (xx.x%) [xx.x, xx.x]	XX
XXXXXXX		xx (xx.x%) [xx.x, xx.x]	XX	xx (xx.x%) [xx.x, xx.x]	XX	xx (xx.x%) [xx.x, xx.x]	XX
	XXXXXXX	xx (xx.x%) [xx.x, xx.x]	XX	xx (xx.x%) [xx.x, xx.x]	XX	xx (xx.x%) [xx.x, xx.x]	XX

95% CI [xx.x, xx.x] Number of Participants (% in parenthesis).

Table 14.4.1.3 Treatment-Related Adverse Events Sorted by SOC and PT

		PraB 40 (n = xx)		PraB 20 (n = xx)		OnaB 20 (n = xx)	
SOC	PT	Participants	Events	Participants	Events	Participants	Events
Any TRAE		xx (xx.x%) [xx.x, xx.x]	XX	xx (xx.x%) [xx.x, xx.x]	XX	xx (xx.x%) [xx.x, xx.x]	XX

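### AE observation stops when the effect is lost, so if 40U lasts longer the crude all-cause AE and SAE percentages and counts will show an excess for 40U even with no true difference

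*SAP*

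**What the plan says.** - **Objective.** Safety shares first place with duration (SAP 1.4): "The primary objectives of this study are to demonstrate the safety and duration of effect of 40U of prabotulinumtoxinA-xvfs".
- **End of follow-up.** SAP 2.1 schedules assessments "every 30 days up to 365 days or until the subject has returned to Baseline as assessed by the Investigator", and the subject then exits. Footnote 3 to Table 1 in both documents and Protocol 4.1 say the same.
- **A floor in one place only.** Protocol 10.2.5 says that on and after Day 90 "subjects are eligible to exit the study once their GLS score at maximum frown has returned to Baseline (Investigator assessment". Protocol 4.1, SAP 2.1 and Table 1 state no earliest exit day. The opening of the SAP says the SAP prevails where the two documents differ.
- **AE window.** Protocol 10.5.6.1 records AEs from injection to the last study visit, and SAP 6.9 reports them to the final visit. SAEs run to 7 days after completion (Protocol 10.5.6.2), which also follows exit.
- **Summaries.** SAP 7.4.1 plans "The number and percentage (incidence) of subjects reporting an AE and the number of AEs will be summarized". Protocol 12.5.1 and SAP 7.4.1 add: "Two-sided Wilson 95% confidence intervals will be calculated for the overall incidence of AEs and SAEs". Table 14.4.1.1 adds a row "Events/Participants", which is per head and not per unit of time. Tables 14.4.1.2 to 14.4.1.7 give subject percentages and event counts only. Neither document plans subject-time, time to first AE, a fixed AE window or a summary of days observed.

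**The concern.** The event that ends AE observation is the primary effectiveness event. If 40U prolongs the effect, as the trial hopes to show, the 40U arm accrues more days in which an unrelated illness or other background AE can be recorded. The whole-study percentages and counts would then mix drug safety with length of observation, and the distortion grows with efficacy. If 40U does raise AE frequency, that excess could not be separated from the longer stay. The Wilson intervals express sampling error only and do not reflect this. What is at stake is the main by-arm summary for a primary objective.

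**Working it through.** **The plan's own figures.** The documents give no figure for time on study. The scenario comes from SAP 7.6: reference median 4 months, 10% annual censoring, hazard ratio (HR) 0.47 at 80% power. Assuming 12 months of follow-up per subject, expected events are 50 × Σ λ/(λ+c) × [1 − exp(−12(λ+c))] = 72.1. Power is then Φ(√(72.1/4) × |ln 0.47| − 1.96) = 89.3% (Schoenfeld), or 86.5% by Freedman's formula. About 7 months of follow-up gives 80.2%. The plan states no follow-up length, so I do not call its 80% an error, and nothing below depends on it.

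**Time on study**
- Reference hazard of return: λ₀ = ln 2 / (4 × 30.4375) = 0.005693 per day. At HR 0.47: λ₁ = 0.002676.
- Loss to follow-up: c = −ln(0.9)/365.25 = 0.000288 per day.
- Return is detected at Days 30, 60, …, 330 and 365. Exit is at detection, not before Day 90 if the floor applies, and at Day 365 at the latest.
- Share due to exit at Day 90 with the floor: 1 − exp(−90λ) = 40.1% against 21.4%. Share due to reach the Day 365 visit: exp(−330λ) = 15.3% against 41.4%.
- Mean observation = Σ pₖ [1 − exp(−c·eₖ)]/c over planned exit days eₖ with probabilities pₖ:

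| Exit rule | Reference | 40U, HR 0.47 | Ratio |
|---|---|---|---|
| Day 90 floor | 175 days | 239 days | 1.37 |
| No floor | 161 days | 232 days | 1.44 |

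At HR 0.7 with the floor the ratio is 1.18.

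**Crude incidence with the same AE rate in both arms**
- Daily rate from the placebo arms in Protocol 1.1 (26.9% and 32.1% over 150 days): r = −ln(1 − p)/150 = 0.002089 and 0.002581.
- Daily rate from the one-year study EV-006 (41.2%): r = −ln(1 − 0.412)/365 = 0.001455.
- Share of subjects with at least one AE = Σ pₖ · r/(r+c) · [1 − exp(−(r+c)eₖ)]. With the floor:

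| AE rate used | Reference | HR 0.7 | HR 0.47 | False excess at 0.7 / 0.47 |
|---|---|---|---|---|
| EV-006, one year | 21.6% | 24.9% | 28.3% | 3.3 / 6.7 points |
| Placebo 26.9%, 150 days | 29.1% | 33.2% | 37.4% | 4.1 / 8.3 points |
| Placebo 32.1%, 150 days | 34.2% | 38.7% | 43.5% | 4.5 / 9.3 points |

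Expected event counts rise in proportion to observation time, so by 37% at HR 0.47. At HR 1 there is no excess.

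**Early-onset AEs.** Take related AEs at 15.4% over 150 days (EV-001). If onset is spread evenly, crude incidence is 17.2% against 22.7%. If all arise in the first 30 days, it is 15.3% in both arms. The documents give no onset timing, so both ends are shown.

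**Does the remedy remove it?** With equal true rates, events per subject-year are 365.25 × r in both arms: 53.1, 76.3 or 94.3 per 100 subject-years for the three rates. A common Day 30 window gives 1 − exp(−30r), about 4% to 7%, in both arms.

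**The case against.** The strongest reply concerns size and consequence, and much of it stands.

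- **Effect size.** HR 0.47 is what 50 per arm could detect. The same section says the study is not powered for inference. A reader might take the 9-point figure as the expected distortion, but the documents do not support that.
- **Constant AE rate.** The placebo 150-day rates, carried forward, imply 53% to 61% of subjects with an AE by Day 365. The one-year studies in Protocol 1.1 report 42.0% and 41.2%, even with repeat injections. These are different studies, but the gap suggests that AEs come early or are reported less later, and either shrinks the excess. Using the 20U active-arm rates (28.5% and 38.2%) gives 8.6 to 10.1 points with the floor, but by the same extrapolation.
- **Which AEs.** A reader might infer that every AE percentage is inflated. Treatment-related AEs and AESIs have their own tables, and relatedness requires a reasonable time sequence. Those that arise soon after injection are hardly affected.
- **No test.** The AE tables have no p-value or difference column, so no type I error is at issue. With 50 per arm a Wilson interval is roughly ±13 points wide.
- **Other tables.** The questionnaire, examination, systems review and vital signs are tabulated by visit, and Table 14.1.4 shows who remains at each visit. These give fixed-time comparisons and make unequal follow-up visible. They do not summarise AEs.

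Imprecision does not cancel a systematic shift, and no planned table relates AEs to time at risk. The mechanism remains.

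**Conclusion.** The point holds for all-cause TEAEs, SAEs and event counts, and only if 40U lasts longer than its comparator. With the Day 90 floor, the false excess is about 7 to 9 percentage points at HR 0.47, about 3 to 5 at HR 0.7, and near zero for AEs that arise soon after injection. Without the floor, observation is more unequal (1.44 against 1.37). The figures rest on exponential duration, detection at scheduled visits, 10% annual loss, and a constant AE rate borrowed from earlier studies.

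The harm is a misleading between-arm contrast in a descriptive summary. It is not a false significance claim, and it does not show that the 40U safety data as a whole are unusable. Nor should a reader assume that Day 90 is a secure common window, since that rests on Protocol 10.2.5 alone.

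**What to change.** In SAP 7.4.1 and the Table 14.4.1 shells, before database lock:

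1. Add by arm, for TEAE, TRAE, SAE and AESI, the number of events and the number of subjects with a first event per subject-year at risk, each with a 95% CI. Time at risk for first events ends at the first event.
2. Add mean and median days observed per arm.
3. Add incidence through Day 30 by arm. Its usefulness does not depend on the Day 90 floor.
4. Keep the crude whole-study tables, with a footnote that observation time depends on loss of effect.
5. Reconcile Protocol 10.2.5 with Protocol 4.1, SAP 2.1 and Table 1 on the earliest exit before using any Day 90 incidence. If the floor does not govern, give a time-to-first-AE estimate at Day 90 that accounts for exit.

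The cost is SAP wording and a few table columns, since visit, exit and AE onset dates are already collected. The Day 30 table omits later AEs, which the per-subject-year table covers. A single rate per subject-year also averages over early and late periods, so the two should be read together.

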7.4.2. Laboratory Variables

The number and percentage of subjects with a clinically significant laboratory abnormality (Investigator opinion) will be summarized for each laboratory test with available normal ranges.

Version 1.1 31-May-2023 Confidential Page 19/58

Descriptive statistics will be used to summarize observed values and changes from Baseline. Shift tables and other tabular and graphical methods may be used to present results for laboratory tests of interest. Listings will be provided with flags indicating clinically significant abnormalities.

7.4.3. Vital Signs

The number and percentage of subjects with a clinically significant vital sign abnormality (Investigator opinion) will be summarized for each parameter; percentages will be based on subjects with non-missing values.

Descriptive statistics will be used to summarize observed values and changes from Baseline. Tabular and graphical methods may be used to present results for parameters of interest. Listings will be provided with flags indicating clinically significant abnormalities.

7.4.4. 12-Lead ECGs

The number and percentage of subjects with a clinically significant ECG abnormality (Investigator opinion) will be summarized for each parameter; percentages will be based on subjects with non-missing values.

Descriptive statistics will be used to summarize results and changes from Baseline. Tabular and graphical methods may be used to present results for parameters of interest. Listings will be provided with flags indicating clinically significant abnormalities.

7.5. Analysis Populations

Three analysis populations are defined: Modified Intent-to-Treat (mITT) Population, Per Protocol (PP) Population, and Safety (SAFT) Population. All analysis populations will be defined and determined prior to database closure and unblinding for the final analysis.

Modified Intent-to-Treat Population

7.5.1. Modified Intent-to-Treat Population

The mITT Population is defined as all subjects who were randomized, received their injection of IP, and have at least one post-dosing assessment for the primary effectiveness endpoint. The ITT principle will be followed in that subjects in the mITT population will be analyzed according to the treatment assigned as per the randomization schedule. The mITT Population will be the primary population used for effectiveness analyses of primary, secondary, tertiary, and exploratory effectiveness endpoints.

7.5.2. Per-Protocol Population

The PP Population is defined as treated subjects who complete the entire study up to the final visit with no protocol deviations that could affect effectiveness assessments. The decision whether a protocol violation/deviation is relevant for the exclusion of subjects from the PP Population will be made in a data review meeting prior to breaking the study blind. The PP Population will be used for supportive effectiveness analyses.

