### 10.2.6 Visit 16 (Final Visit or ET Visit; Day 365 ±14 days)

The Final visit (or ET visit) will take place when subjects GLS score (Investigator assessment) has returned to Baseline. Subjects may withdraw from participation in the study at any time for any

reason. If withdrawal occurs, the subject should be asked to complete a follow-up or early termination visit, if possible. During the final or early termination visit, both safety and effectiveness evaluations will be performed as follows:

- Brow Area Photography
- UPT (if female subject of childbearing potential)
- Effectiveness Evaluations Investigator (Blinded Evaluator)
  - GLS (max frown)
  - GAIS
- Effectiveness Evaluations Subject
  - GLS (max frown)
  - GAIS
  - Subject Satisfaction
  - Clinical Interview
- Safety Assessments Investigator (Blinded Evaluator)
  - Directed Questionnaire
  - Directed Review of Systems
  - Vital Signs
  - Physical Exam
  - Clinical Laboratory Tests
  - ECG
  - Concomitant Medications
  - Adverse Events

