#### 11.2 Subject Completion

A subject will be considered to have completed the study if he/she has completed all assessments and applicable study visits or experienced an event that precludes further study participation.

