7. STATISTICAL METHODS

7.1. Primary Effectiveness Endpoint

The primary effectiveness endpoint will be duration of effect (regardless of responder status), defined as the number of days from Treatment Day (Baseline) to the day that GLS severity (Investigator assessment) at maximum frown returns to the Baseline value. Although the trial is not powered for inferential analysis, this will be the most influential outcome in the overall assessment of the effectiveness of prabotulinumtoxinA 40 Units, compared to prabotulinumtoxinA 20 Units, in treating moderate to severe glabellar lines. Analysis will be performed using the modified Intent-To-Treat (mITT) population and regardless of responder status.

Duration of effect will be described by Kaplan-Meier curves and the respective median times with associated 2-sided 95% confidence interval (CI) for each treatment group. Statistical analyses of treatment group differences will be done using Cox proportional hazards regression with time to return to Baseline as the dependent variable, treatment group as the independent variable, and age, gender, and Baseline GLS score (Investigator assessment) at maximum frown as covariates.

Statistical significance will be established at the 0.025 level with one-sided hypothesis testing.

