7.7. General Considerations

Data will be listed by subject number. Data will be summarized by treatment and study visit, where applicable. For categorical parameters, the number and percentage of subjects/observations in each category will be presented; percentages will be based on the number of subjects in the relevant analysis population in each treatment group. For continuous parameters, descriptive statistics will include n (number of subjects or observations), mean, standard deviation, median, and range. A full description of the statistical methods planned for this study will be provided in the Statistical Analysis Plan (SAP). All programs for data output and analyses will be written in SAS version 9.4 or higher (SAS Institute, Inc., Cary, NC).

Missing Values: For the mITT analysis of primary, secondary, tertiary, and exploratory duration of effectiveness endpoints, in the case of a missed visit, subjects will be considered to have returned to Baseline if they are confirmed to have returned to Baseline at the next non-missed visit. Subjects will be considered to have to have returned to Baseline if they fail to attend 2 consecutive visits or drop out of the study. For missing observations for exploratory endpoints other than duration of effect data will be analyzed as observed without imputation.

Discontinuation and Drop-Outs: Dropouts will not be replaced. Subject disposition will summarize the number of subjects who were randomized and who discontinued from the study (including reasons for discontinuation).

Interim Analysis: An interim analysis will be conducted when >90% of subjects have completed Visit 8 (Day 120) to evaluate response to exposure (efficacy, duration) and adverse events. For assessment of the primary effectiveness endpoint, 95% CIs will be presented but statistical analyses will not be conducted and a statistical penalty for the final analysis will not be employed. While data by treatment group will be presented, individual subjects will not be unblinded.

Poolability of Investigative Sites: Data from all investigative sites will be pooled based on the assumption of clinical comparability: the same protocol will be used for all sites, all sites will be monitored for protocol compliance, and the same data collection instrument and methodology will be used across all sites.

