14.1 Subject Disposition

Table 14.1.1 Enrollment

Site	Screened	Screen Failures	Randomized	PP	ITT	SAFT
01	XX	XX	XX	XX	XX	XX
02	XX	XX	XX	XX	XX	xx
03	XX	XX	XX	XX	XX	XX
04	XX	XX	XX	XX	XX	xx
05	XX	XX	XX	XX	XX	XX
All sites	XX	XX	XX	XX	XX	XX

Number of subjects

Table 14.1.2 Subject Discontinuations with Primary Reason

Study Exit		PraB 40 (n = xx)	OnaB 20 (n = xx)	PraB 20 (n = xx)
Completion of Study	N	XX	XX	XX
	Completed up to return to BL	xx (xx.x%)	xx (xx.x%)	xx (xx.x%)
Primary Reason for d/c* prior	N	xx (xx.x%)	XX	XX
to return to BL	Adverse Event	xx (xx.x%)	xx (xx.x%)	xx (xx.x%)
	Lost to follow- up	xx (xx.x%)	xx (xx.x%)	xx(xx.x%)
	Withdrew consent	xx (xx.x%)	xx (xx.x%)	xx (xx.x%)
	Protocol violation	xx (xx.x%)	xx (xx.x%)	xx (xx.x%)
	Investigator Decision		xx (xx.x%)	xx (xx.x%)
	Other		xx (xx.x%)	xx (xx.x%)

Number of subjects (% in parenthesis). *d/c= discontinuation

Table 14.1.3 Listing of Subject Discontinuations

Subject	Treatment	Gender*	Age	Last Visit	Primary Reason for
Number	Group				Discontinuation
##-###	PraB 40	M/F	XX	V#	xxxxxxxxxxxxxxxx
##-###	PraB 20	M/F	XX	V#	xxxxxxxxxxxxxxx
##-###	OnaB 20	M/F	XX	V#	xxxxxxxxxxxxxxxx
##-###	OnaB 20	M/F	XX	V#	xxxxxxxxxxxxxxx
##-###	PraB 40	M/F	XX	V#	xxxxxxxxxxxxxxxx
##-###	PraB 20	M/F	XX	V#	xxxxxxxxxxxxxxx
##-###	PraB 40	M/F	XX	V#	XXXXXXXXXXXXXXXX
##-###	OnaB 20	M/F	XX	V#	XXXXXXXXXXXXXXXX

M=Male, F=Female

Version 1.1 31-May-2023 Confidential Page 24/58

Table 14.1.4 Subject Disposition per Visit

Disposition of Subjects at	PraB 40	OnaB 20	PraB 20
each Study Visit	(n = xx)	$(\mathbf{n} = \mathbf{x}\mathbf{x})$	$(\mathbf{n} = \mathbf{x}\mathbf{x})$
N	XX	XX	XX
V1 (screening)	xx (xx.x%)	xx(xx.x%)	xx(xx.x%)
V2 (pre-Tx)	xx(xx.x%)	xx(xx.x%)	xx (xx.x%)
V3 (48hr)	xx(xx.x%)	xx(xx.x%)	xx(xx.x%)
V4 (D7; phone f/u)	xx(xx.x%)	xx(xx.x%)	xx (xx.x%)
V5 (D30)	xx (xx.x%)	xx (xx.x%)	xx(xx.x%)
V6 (D60)	xx(xx.x%)	xx(xx.x%)	xx(xx.x%)
	xx(xx.x%)	xx(xx.x%)	xx (xx.x%)
	xx (xx.x%)	xx (xx.x%)	xx (xx.x%)
V16 (D365)	xx (xx.x%)	xx (xx.x%)	xx (xx.x%)

Number of subjects (% in parenthesis)

Table 14.1.5 Study Dates

FPFV	LPFV	LPLV	Enrollment Duration	Study Duration
dd-mmm-yyyy	dd-mmm-yyyy	dd-mmm-yyyy	XXX	XXX

FPFV= First Patient First Visit, LPFV= Last Patient First Visit, LPLV= Last Patient Last Visit. Enrollment duration=FPFV-LPFV+1, Study duration=FPFV-LPLV+1

Confidential Page 25/58

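### The Per Protocol population requires study completion, so it deletes dropouts from a time-to-event analysis and modestly shortens the estimated durations; neither planned population censors them

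*SAP*

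**What the plan says.** SAP 7.5.2 and Protocol 12.6.2 define PP in the same words: "treated subjects who complete the entire study up to the final visit with no protocol deviations that could affect effectiveness assessments". Its role is stated too: "The PP Population will be used for supportive effectiveness analyses". For the primary endpoint, SAP 7.1 says: "Analysis will be performed using the modified Intent-To-Treat (mITT) population and regardless of responder status".

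The end of follow-up depends on the outcome. Protocol 10.2.6 says: "The Final visit (or ET visit) will take place when subjects GLS score (Investigator assessment) has returned to Baseline". The same visit is labelled Day 365, and SAP 2.1 ends assessment at 365 days or at return to Baseline.

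Dropouts are not censored in mITT. SAP 7.7 treats subjects as returned to Baseline "if they fail to attend 2 consecutive visits or drop out of the study". The sample-size text (SAP 7.6, Protocol 12.7) nevertheless assumes exponential censoring times at 10% a year.

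Completion is described in two other places. Protocol 11.2 covers a subject who has "completed all assessments and applicable study visits or experienced an event that precludes further study participation". In the SAP's disposition shell (Table 14.1.2) the only completion row is "Completed up to return to BL", with no row for a subject still in effect at Day 365.

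**The concern.** Requiring completion conditions the analysis on something that happens after randomisation and is tied to the endpoint. A subject whose effect ends at month 3 has three months in which to drop out; one whose effect lasts a year has twelve. Among subjects who would otherwise be followed fully, those who drop out therefore tend to have longer durations, and deleting them shortens the Kaplan-Meier curve. This needs no link between dropout and effect.

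At stake is the value of PP as a supporting analysis. If mITT and PP both shorten duration, their agreement says little about whether dropout matters. There is also a wording gap: if completion were read from Table 14.1.2 alone, subjects still in effect at Day 365 would leave PP as well, and that would distort the comparison badly.

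**Working it through.** **Inputs.** From SAP 7.6: 50 per arm, exponential failure and censoring, reference median 4 months, hazard ratio 0.47, 10% annual censoring. Hence λ20 = ln 2/4 = 0.1733 per month, λ40 = 0.47 × 0.1733 = 0.0814 (median 4/0.47 = 8.51 months) and c = −ln(0.9)/12 = 0.00878. Follow-up stops at 12 months. My assumptions: dropout is independent of effect with the same hazard in both arms, and 20% a year (c = 0.0186) is used as a second value. Days are months × 30.

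**The plan's own figure.** Expected events = 50 × Σ λ/(λ+c) × (1 − exp(−12(λ+c))) = 42.2 + 29.8 = 72.1. Schoenfeld power = Φ(√(72.1/4) × |ln 0.47| − 1.96) = Φ(1.245) = 89.3%, against the stated 80%. Freedman gives 86.5%. Variants near 80% need an input the plan does not state, such as six months of accrual within a 12-month total (Freedman 81.5%). The stated figure is conservative, and nothing below depends on it.

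**Share deleted from PP.** p = c/(c+λ) × (1 − exp(−12(c+λ))).
- 10%, 20U: 0.0482 × 0.8875 = 4.3%, or 2.1 of 50.
- 10%, 40U: 0.0973 × 0.6613 = 6.4%, or 3.2 of 50.
- 20%: 8.7% (4.4) and 13.0% (6.5). With the onabotulinumtoxinA arm behaving like 20U, the total is 4.4 + 4.4 + 6.5 = 15.3, close to the 15 implied by 135 evaluable of 150 in Protocol 11.3.

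**PP median.** A completer either returns to Baseline before dropping out or is still in effect at month 12. With s = λ + c, the PP curve is [λ/s × (exp(−st) − exp(−12s)) + exp(−12s)]/(1 − p). The median is where this equals 0.5.

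**mITT rule.** If dropout is an event, the hazard is λ + c, the median is ln 2/(λ+c), and at 10% the hazard ratio is (0.0814 + 0.00878)/(0.1733 + 0.00878) = 0.496.

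| Annual dropout | Handling | Median 20U, 40U (months) | Days short | Hazard ratio |
|---|---|---|---|---|
| any | censored | 4.00, 8.51 | 0, 0 | 0.470 |
| 10% | PP | 3.84, 8.10 | 5, 12 | 0.476 |
| 10% | mITT | 3.81, 7.68 | 6, 25 | 0.496 |
| 20% | PP | 3.67, 7.64 | 10, 26 | 0.483 |
| 20% | mITT | 3.61, 6.93 | 12, 47 | 0.521 |

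The PP hazard ratios are large-sample Cox values; simulation with 400,000 per arm gave 0.478 and 0.484. Across 5% to 30% annual dropout, the PP hazard ratio stays between 0.47 and 0.49.

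In 10,000 simulated trials of 50 per arm at 10% dropout, power was 89.3% with censoring, 87.9% for PP and 86.7% for the mITT rule. With a true hazard ratio of 1, each rejected about 2.3% of the time.

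**If completion meant only return to Baseline.** Before dropout, exp(−12 × 0.1733) = 12.5% of 20U and exp(−12 × 0.0814) = 37.6% of 40U are still in effect at month 12. Removing them too gives a hazard ratio of about 0.76, medians near 3.2 and 4.4 months, and power of about 21%.

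**The case against.** The best opposing case is that this is too small to matter. Visits are 30 days apart with ±7-day windows, so the shifts are under half a visit interval at 10% dropout and under one at 20%. PP is supportive, Appendix A of the SAP has no PP efficacy table (PP appears only as a count in Table 14.1.1), and the study is described as not powered for inference. All of this stands and fixes the point as minor.

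PP is also closer to the truth than mITT here (0.476 against 0.496), and it handles dropouts differently, so comparing the two shows something about the dropout-as-event rule. That stands: the comparison is weak evidence, not worthless. Other supporting results exist as well, such as unadjusted hazard ratios and log-rank tests in the primary table and post hoc COVID-19 analyses (Protocol 12.8). None of them is specified to censor dropouts.

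The direction depends on the model. If subjects leave because the effect was poor or waning, deleting them could lengthen PP durations. Protocol 10.2.5 also permits exit only from Day 90. If early returners must stay until then, deletions at 10% become 2.4 and 3.4 of 50, a gap below one subject.

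Stronger readings are tempting but unsupported:
- A reader might infer that PP strips out long-duration subjects as such. It strips out dropouts; on the natural reading, a subject followed to Day 365 has reached the final visit and stays in.
- A reader might infer that the 40U arm is known to lose more subjects. The documents do not say so. It follows only if 40U lasts longer and dropout hazards are equal, and then amounts to about one subject at 10%.
- A reader might see a conflict between Protocol 11.2, which counts a precluding event as completion, and the withdrawals in 11.3. PP requires reaching the final visit and does not invoke 11.2, so no subject's PP status clearly changes.

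**Conclusion.** The point holds as a minor one. The PP definition selects on completion, which is tied to the duration being measured. Under 10% to 20% annual dropout, independent of effect, with equal hazards and a hazard ratio of 0.47, it shortens PP medians by about 5 to 10 days at 20U and 12 to 26 days at 40U. It moves the hazard ratio to about 0.475 to 0.485, toward no difference, with no type I error inflation in simulation and no effect on the primary mITT analysis.

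The more useful conclusion is the gap this exposes. The sample size assumes dropouts are censored, mITT scores them as events and PP deletes them. Both planned treatments shorten duration under these assumptions, so their agreement would be only weak reassurance. The hazard ratio of about 0.76 belongs solely to a literal reading of the disposition shell. A reader might infer that the plan intends it, but the Day 365 final visit points the other way; it is a wording risk to close, not an expected result.

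**What to change.** In SAP 7.5.2 and Protocol 12.6.2:
- Define PP as randomised subjects who met eligibility, received the assigned injection as specified, and had no deviation affecting effectiveness assessments. Say that withdrawal alone is not such a deviation.
- Delete the requirement to complete to the final visit.
- Keep withdrawn subjects in PP, censored at their last valid Investigator GLS.
- State that a subject still in effect at Day 365 is a completer, censored at that visit, and add that row to Table 14.1.2.

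The cost is SAP and protocol wording, one derived censoring date and one shell row; no subjects or visits are added. The remaining weakness is that censoring at withdrawal relies on dropout being non-informative, which should be stated beside the result. Because mITT keeps its dropout-as-event rule, the two analyses would then bracket different assumptions about dropout.
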